1.0 OBJECTIVES

Diabetes is a major health care problem in our country and contributes to the development of severe co-morbidities, including coronary artery disease, heart failure, stroke, renal failure and many others. Whereas the etiology of diabetes is multifactorial, patients with chronic pancreatitis or recurrent acute pancreatitis may acquire insulin-dependent diabetes due to islet cell destruction. Islet cell autotransplantation is the optimal therapeutic approach for many of these patients.

Islet cell autotransplantation is typically done by excision of the pancreas, followed by isolation of the islet cells and then infusion of these cells into the sinusoids of the liver. Isolation of the islet cells occurs in an ischemic and hypoxic environment, resulting in ischemia reperfusion (IR) injury and destruction of islet cells following infusion into the sinusoids. Hence, strategies to prevent IR injury and subsequent islet cell destruction, such as the administration of inhaled nitric oxide (NO) or sodium nitrite (NaNO_2), could enhance islet cell survival following reperfusion, thereby decreasing long-term insulin requirement.

The anion nitrite (NO_2^-) releases NO in biological systems and has been demonstrated to inhibit IR injury (REFS) and improve outcomes (REFS) in patients undergoing Liver transplantation. The objective of this study is to determine whether the NO donor, nitrite will prevent I/R injury and reduce long-term insulin requirements in patients receiving islet cell autotransplantation.

The **central hypothesis** is that in patients undergoing islet cell autotransplantation, infusion of nitrite will inhibit islet cell destruction. The hypotheses of the specific aims are that nitrite will:

- 1) Increase diabetes cure rate - decrease the amount of and/or the need for long-term insulin requirement.
- 2) Decrease the ischemic injury during islet cell procurement,
- 3) Decrease IR injury following islet cell infusion, and

The purpose of this study is to act as a preliminary or “pilot” study. If the data obtained affirm the central hypotheses, further investigations will be conducted to determine mechanism and clinical efficacy.

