3.0 ELIGIBILITY CRITERIA

All patients will be enrolled into the study at the University of Alabama at Birmingham Medical Center (UAB). Approximately 18 islet cell autotransplantations are conducted at UAB annually by one surgeon, thereby eliminating the need to include surgical technique as a possible confounding variable.

Based on our prior experience conducting similar studies, we anticipate that approximately 80% of patients undergoing islet cell autotransplantation meet enrollment criteria and agree to the written informed consent. Accordingly, we conservatively estimate that it will take approximately two years to complete enrollment for the study, followed by a third year for data analysis and study closeout.

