5.0 EXPERIMENTAL PROTOCOL

Protocol Design:

This is a single institution, randomized, placebo-controlled clinical study. There will be 3 cohorts: control group, pre-isolation nitrite infusion, and a post-isolation (reinfusion) cohort.

After induction of general anesthesia with propofol (1-1.5 mg/Kg), tracheal intubation, the establishment of central venous access, invasive monitors and maintenance anesthesia with sevoflurane (1-1.5 minimum alveolar concentration) in 50:50 oxygen: air, infusions will be administered based on the randomization assignment.

I. Control Group A placebo (saline infusion) will be administered during the pre-isolation phase and during the reinfusion phase.

II. Pre-Isolation Infusion Group

[figure not shown]

Figure 1: Pre-isolation group schematic: Sodium nitrite will be initiated (pre-isolation infusion group) during the pre-isolation phase. Saline will be administered during the reperfusion period.

III. Post-Isolation (Reinfusion) Group

[figure not shown]

Figure 2: Reinfusion group schematic: Saline will be administered during the pre-isolation period. Sodium nitrite infusion will be initiated just prior to the reinfusion.

For all 3 groups:

Intraoperative arterial and venous blood samples (BS) will be drawn immediately prior to initiation of the infusion (BS1), 5 min prior to infusion of Islet Cells (BS2), 20 min after infusion of Islet Cells (BS3), and 40 min after infusion of Islet Cells (BS4).

Postoperative blood samples will be obtained 24, 48, 72 and 96 hours after the completion of surgery.

Results of routine lab work performed at the routine 3 month follow-up visit will be collected.

Procedure for Sample collection (email from [name] 6/28/16) – to be performed by lab tech in BMR

- 1) *Transferring blood to Eppendorf tubes,*
- 2) *Centrifuging (using a table top min-fuge which we can provide),*
- 3) *Transferring plasma to 4 other vials (1 containing a pre-made solution, which we can provide) and flash freezing all vials in liquid N₂*
- 4) *Taking some of the red cell pellet and adding to vials (containing pre-made solution that we can provide) and flash freezing all vials in liquid N₂*
- 5) *All samples need to be stored at -80C.*

Primary Endpoints:

- Markers of pancreatic function:
 - Blood glucose levels
 - HbA1c levels pre-operatively and at the 3 month post-operative visit
 - Exogenous insulin use
 - Measured from blood samples 24, 48, 72, 96 hours post op & at 3 months post op

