- Decrease in reperfusion injury
- Incidence of diabetes post-operatively

Intraoperative blood samples will be analyzed for serum and methemoglobin levels and biochemical markers of oxidative and nitrosative stress, including plasma and hepatic 3-nitrotyrosine, oxidized lipids (isoprostanes, 8-epi-PGF₂α), protein carbonyls and the NO-metabolites, nitrite, nitrate, S-nitrosothiols, C-N-nitroso compounds and heme nitrosyls. If the above processing is not part of the costs, and assuming 30 patients, each with 6 blood draws then running assays for plasma and red cell NOx, C-peptide levels, circulating pro-inflammatory chemokines/cytokines and perform immunophenotyping of monocytes and neutrophils by flow cytometry and mRNA accumulation.

	Sample Name	Blood Glucose	HbA1c	Insulin level exogenous	RF	C-peptide	Circ pro-inflammatory chemokine / cytokines	Immunophenotyping monocytes and neutrophils	mRNA				
Intraoperative													
Prior to infusion	BS1	X	X			X	X	X	X				
5 min prior to Islet cell infusion	BS2	X											
20 mins after infusion of Islet cells	BS3	X											
40 mins after infusion of Islet cells	BS4	X											
Post-op													
24 hours	BS5	X		X		X	X	X	X				
48 hours	BS6	X		X		X	X	X	X				
72 hours	BS7	X		X		X	X	X	X				
96 hours	BS8	X		X		X	X	X	X				
Follow up													
Clinic visit 3 months post-op	BS9	X	X	X		X	X	X	X				

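### The long-term insulin and cure part of the objective cannot be answered, because no outcome is scheduled after 3 months

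*Combined protocol and SAP*

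**What the plan says.** **The question.** Section 1.0 gives the objective two parts: to prevent ischemia-reperfusion injury, and to "reduce long-term insulin requirements in patients receiving islet cell autotransplantation". Aim 1 is to raise the diabetes cure rate, which it explains as to "decrease the amount of and/or the need for long-term insulin requirement". Section 2.3 returns to the same theme, saying that nitrite may lower long-term insulin need and perhaps raise the rate of cure. Section 1.0 also describes the study as a pilot and leaves mechanism and clinical efficacy to later work.

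**The measurements.** Under the primary endpoints in section 5.0, the markers of pancreatic function, including exogenous insulin use, are "Measured from blood samples 24, 48, 72, 96 hours post op & at 3 months post op". HbA1c is listed as "HbA1c levels pre-operatively and at the 3 month post-operative visit". On follow-up, the section says: "Results of routine lab work performed at the routine 3 month follow-up visit will be collected". The last row of the sampling table is BS9, "Clinic visit 3 months post-op". Post-operative incidence of diabetes is also an endpoint, but it has no definition and no time point.

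**The timetable and analysis.** Section 3.0 allows about two years for enrolment, "followed by a third year for data analysis and study closeout". Section 7.0 names no analysis of long-term insulin need or of cure.

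**The concern.** The objective determines what the trial may conclude. Here part of it concerns a horizon at which nothing is observed. Whether a patient needs insulin at 3 months and whether that patient needs it in the long run are different questions, and the plan gives no rule for getting from one to the other. It neither says how long *long-term* is nor designates the 3-month value as its measure. If the 3-month comparison favours nitrite, the wording of the objective leaves room to present it as a lasting reduction in insulin need or as cure, although the data would show neither.

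**Working it through.** **Step 1. Set the question against the schedule.**

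| Element | Where | Latest scheduled time |
|---|---|---|
| Long-term insulin requirement (objective, Aim 1) | Section 1.0 | Exogenous insulin use: 3 months |
| Diabetes cure rate (Aim 1) | Section 1.0 | No endpoint of that name; the nearest, incidence of diabetes, is undated |
| Blood glucose | Section 5.0 | 3 months |
| HbA1c | Section 5.0 | 3 months (also pre-operative) |
| Any blood sample | Section 5.0, sampling table | BS9, 3 months |

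**Step 2. Count the post-operative times.** They are 24, 48, 72 and 96 hours and 3 months, five in all. Within 96 hours: 4/5 = 80%. At 3 months: 1/5. After 3 months: 0. The undated diabetes endpoint does not change the count, because no later visit exists at which it could be assessed.

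**Step 3. What the schedule can answer.** Insulin use at 3 months is observed. Aims 2 and 3 concern injury during procurement and after islet infusion, and they do not depend on follow-up beyond 3 months. Only the long-term and cure part is left without data.

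**Step 4. Could a 12-month look fit the timetable?** The 12-month horizon is an assumption for illustration and is not in the documents. Also assumed are even accrual from month 0, surgery at enrolment and no losses. The planned sample is 3 × 10 = 30, as sections 4.1 and 7.0 state. A patient reaches 12 months by month 36 only if enrolled by month 24, so the number doing so is 2 × the yearly enrolment, up to 30.

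| Yearly enrolment | Source | Years to enrol 30 | Reach 12 months by month 36 |
|---|---|---|---|
| 18 × 0.80 = 14.4 | Section 3.0 | 30/14.4 = 2.08 (25 months) | 2 × 14.4 = 28.8, about 28–29 |
| 10 | Section 7.0, all enrol | 30/10 = 3.0 | 20 |
| 8 | Section 7.0, all enrol | 30/8 = 3.75 | 16 |
| 10 × 0.80 = 8.0 | Section 7.0 with section 3.0's 80% | 30/8.0 = 3.75 | 16 |
| 8 × 0.80 = 6.4 | Section 7.0 with section 3.0's 80% | 30/6.4 = 4.69 | 12.8, about 13 |

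At section 3.0's rate the last patient reaches 12 months at about month 25 + 12 = 37, after the third year ends. At section 7.0's figures, enrolment alone fills or overruns the three years. A 12-month outcome would therefore cover about 28–29 patients at best and about 13–20 at the lower rates. A count taken at month 36 itself also leaves no time for analysis.

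**The case against.** The strongest reply is that this is a labelling matter in a pilot. Section 1.0 states hypotheses rather than results and defers clinical efficacy to later studies. Section 5.0 gives the 3-month time openly. *Long-term* is undefined, so 3 months is not expressly excluded. No rule in the documents says that a 3-month difference will be reported as cure.

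Much of this stands, and it lowers the severity. It does not remove the mismatch. Pilot status explains a small sample, but the pilot's own objective is still to determine whether long-term insulin need falls. If the 3-month value is meant to serve as the long-term measure, the plan has to say so, and it does not.

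A reader might infer more than the documents support:

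- **That the trial's question as a whole cannot be answered.** The injury part of the objective, Aims 2 and 3, and insulin use at 3 months are untouched by the length of follow-up.
- **That the protocol already claims a long-term effect, or will report one.** It states an objective and hypotheses, and it contains no reporting rule. Over-interpretation is a risk left open by the wording, not a stated intention.
- **That the third year makes 12-month data on all 30 patients readily available.** Step 4 shows otherwise, and the only routine visit mentioned is the one at 3 months.
- **That the third year holds no patient data.** At section 3.0's rate, patients enrolled in the last three months of year 2, about 14.4 × 3/12 = 3.6, have their 3-month visit in year 3. What is absent is any planned assessment beyond month 3.

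**Conclusion.** The point holds for the long-term and cure component of the objective and Aim 1, and for that component only. Its size is a count: no scheduled outcome after 3 months, and one post-operative time out of five later than 96 hours. This follows from sections 1.0 and 5.0 directly and needs no assumption about effect size or power. It also does not depend on the 12-month calculation, which bears only on the optional addition below. The mismatch should be corrected because it changes what the trial may conclude. In a pilot whose injury aims and 3-month insulin data remain usable, it is not a fatal defect.

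**What to change.** **Main change.** Restate the objective and Aim 1 as exogenous insulin requirement and insulin independence at 3 months. Have the investigators define insulin independence in advance, and give the diabetes-incidence endpoint the same 3-month date. Drop *long-term* and *cure* from the objective, Aim 1 and the conclusion, so that the conclusion goes no further than 3 months. Bring the matching sentence in section 2.3 into line as background expectation rather than something this study will show. The cost is a few words; no visit, sample or patient is added. The downside is a narrower claim.

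**Optional addition.** Where later clinic records exist, extract insulin dose and insulin-free status at about 12 months as a descriptive secondary outcome. State the number of patients with a record in each arm and the reasons for missing records. The cost is one chart review for each patient with a record, and incomplete data must be expected. Whether such records exist at this site should be confirmed before the outcome is written into the plan.

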2.0 BACKGROUND & RATIONALE

2.1 Scope of the Public Health Problem

Diabetes is a significant medical problem for patients, as it can lead to multiple other medical problems i.e. Coronary Artery Disease, Vascular Disease, and Kidney Disease. National statistics indicate that 25.8 million people have diabetes in the US. Approximately 18 million people have been diagnosed with an additional 7 million people yet to be diagnosed. Some 215,000 people under the age of 20 have the disease. Among people over the age of 20, about 1.9 million were diagnosed in 2010. After the age of 65, 26.9% of people have diabetes. The estimated costs in 2007 were \$174 Billion dollars with \$58 Billion dollars being indirect costs i.e. disability, work loss, and premature mortality.

In type 2 diabetes, the body either doesn't produce enough insulin or is unable to utilize it. Without enough insulin, cells are unable to use glucose for energy production. Over time the high blood glucose levels cause microvascular and/or macrovascular damage. Type 2 diabetes complications include cardiovascular disease, cerebrovascular disease, kidney failure, retinopathy, and neuropathy. Diabetes is the leading cause of kidney failure, non-traumatic limb amputation, and new onset blindness in adults in the U.S. Diabetes is the seventh leading cause of death in the U.S. The risk of death is twice the non-diabetic patient at the same age.

In patients with chronic pancreatitis or recurrent acute pancreatitis, Islet Cell transplantation may lead to a cure of their Diabetes related to the resection of the Pancreas. In patients undergoing Islet Cell Auto Transplantation, the removal of the pancreas and the retrieval of the islet cells produces a hypoxic environment. This process leads to Ischemic Reperfusion (IR) injury of the islet cells. Hence, strategies to prevent IR injury, including inhaled Nitric Oxide (NO) and Sodium Nitrite (NaNO₂) are being tested. For example, replenishing NO via therapeutic administration may serve to abrogate reperfusion injury in these vulnerable patients.

2.2

Chronic pancreatitis is the progressive and irreversible destruction of the pancreas characterized by inflammation and fibrosis that initially results in exocrine deficiency, but can progress to endocrine dysfunction. This disease often follows a chronic relapsing pattern with patients experiencing intermittent anorexia, nausea, vomiting, and abdominal pain. As the disease becomes severe, many patients become malnourished and develop debilitating chronic abdominal pain.^{1,2,3} The most common etiology of chronic pancreatitis in Western society is alcohol consumption, comprising 70% to 90% of cases.⁴ Other causes include biliary obstruction, pancreatic division, trauma, hypertriglyceridemia, hereditary, idiopathic, and autoimmune pancreatitis.⁵

Total or completion pancreatectomy is the surgical treatment for patients with small duct disease, diffuse glandular involvement, or recurrent pain after a previous operation for chronic pancreatitis.⁶ Due to the resulting apancreatic state, patients undergoing total pancreatectomy are rendered insulin dependent diabetic. Unlike Type I insulin dependent diabetics, apancreatic patients are deficient in insulin, glucagon, and pancreatic polypeptide. Peripheral insulin receptors are upregulated, enhancing insulin sensitivity⁷ while the absence of glucagon causes patients to be prone to wide variations in serum glucose levels.^{8,9} Pancreatic polypeptide deficiency may contribute to difficulty in glycemic control by increasing hepatic resistance to insulin. This difficult to control and often unstable metabolic state is commonly referred to as "brittle diabetes".^{10,11}

Pancreatic islet cell autotransplantation at the time of total or completion pancreatectomy can be effective in preventing or minimizing pancreatogenic diabetes.^{12,17} Sutherland et al. performed the first successful total pancreatectomy with islet cell autotransplantation in 1977.¹³ Since that time, techniques have been refined and technology improved. Experience at the University of Minnesota demonstrated a rate of insulin independence of 71% after autotransplant in those

without a previous pancreatic or abdominal operation. Only 18%-20% of patients who had undergone a previous Puestow drainage or distal pancreatectomy were insulin independent.¹⁴ Islet yield is a strong predictor of postoperative insulin independence, with best results obtained when greater than 300,000 islet cells¹³ or >2500 Islet cells/kg¹⁴ are transplanted. Timing of islet cell autotransplant becomes a factor since 3 of 4 patients with chronic pancreatitis will develop diabetes in less than 6 years after developing the disorder.¹⁵ Some authors have recommended earlier total pancreatectomy with islet cell autotransplant for causes of pancreatitis including hereditary pancreatitis¹⁶ which may increase islet cell yield and rate of postoperative insulin independence.

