4.2 Randomization Procedure

This is a single institution, blinded, placebo-controlled clinical trial. Patients will be randomized to one of three (3) arms of the study by the research pharmacist:

- Control group (saline infusion will be administered during the pre-isolation and post-isolation phases)

- Pre-isolation infusion (nitrite infusion will be administered during the pre-isolation phase and saline will be administered during the post-isolation phase)
- Post-isolation (saline will be administered during the pre-isolation phase and nitrite infusion will be administered during the reperfusion phase)

Continuous infusion of 32 mg sodium nitrite in 100 mL normal saline at a rate of 10 mL per min over for the duration of the surgery, which are calculated to achieve steady-state plasma concentrations of approximately 10 μ M, concentrations shown to have therapeutic efficacy in animal models of IRI.

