7.0 STATISTICAL CONSIDERATIONS

Primary Study Variables include: Demographics (age, gender, pre-operative weight, pre-operative BMI,

General Data Analysis: All anthropometric data will be compared using unpaired Student's t-test. Length of stay data will be compared using Cox proportional hazard

analysis. All other data will be compared using one-way repeated measures ANOVA with post-hoc analysis by unpaired Student's t-test or Chi Square analysis as appropriated. For all comparisons, a value of $p < 0.05$ will be considered significant.

This is a pilot study. We plan to enroll 10 patients in each of the 3 arms of this study (total N=30).

Study Population Availability: Approximately 8-10 patients present to UAB for this procedure annually. Potential study subjects will be identified by [name] and his clinic team.

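### Section 7.0 names no baseline covariate, although the background reports 71% versus 18%-20% insulin independence by surgical history: a loss of precision at 10 per arm, not a bias

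*Combined protocol and SAP*

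**What the plan says.** **Background.** The text under the heading number 2.2 describes one centre's experience: "a rate of insulin independence of 71% after autotransplant in those" patients "without a previous pancreatic or abdominal operation". The next sentence gives the contrast: "Only 18%-20% of patients who had undergone a previous Puestow drainage or distal pancreatectomy were insulin independent". It then adds that "Islet yield is a strong predictor of postoperative insulin independence".

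**Population.** Section 2.2 counts recurrent pain after earlier surgery for chronic pancreatitis among the indications for total or completion pancreatectomy. Section 3.2 excludes only liver disease and unsuitability for surgery. Previously operated patients can therefore enter. Section 3.1 describes the sample as adults who already have acquired insulin-dependent diabetes.

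**Allocation.** Section 4.2 states: "Patients will be randomized to one of three (3) arms of the study by the research pharmacist". It mentions no strata, blocks or minimisation.

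**Analysis.** Section 7.0 sets the size: "We plan to enroll 10 patients in each of the 3 arms of this study (total N=30". It gives anthropometric data a t-test and length of stay a Cox model. For the rest: "All other data will be compared using one-way repeated measures ANOVA with post-hoc analysis" by t-test or chi-square, at p < 0.05. No sentence on analysis names a covariate. The list of study variables breaks off after BMI, so surgical history may be collected; the text does not show.

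**Endpoints.** Section 5.0 lists blood glucose, HbA1c, exogenous insulin use, reperfusion injury and post-operative diabetes. Section 1.0 makes reduced or absent long-term insulin need the first hypothesis.

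**The concern.** The plan cites a factor, fixed before randomisation, that goes with a gap of more than 50 points in an outcome close to its first hypothesis, and then makes no use of it. In a large trial this would matter little. With 10 per arm, the number of previously operated patients can easily differ between arms by three or four. An unadjusted analysis then carries that difference as noise in the treatment estimate.

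Section 1.0 says that further work will follow if the data affirm the hypotheses. The estimated differences will therefore inform a decision, and any precision that can be had cheaply is worth having.

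**Working it through.** The plan gives no power calculation, effect size or standard deviation. The only stated figure to reproduce is 3 × 10 = 30.

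**Inputs.** From section 2.2: 71%, and 18%-20% (midpoint 19% below). From section 7.0: 10 per arm. Assumed, because the documents do not give it: 20-50% previously operated, that is K = 6, 9, 12 or 15 of 30.

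**Step 1: the gap.** 71 − 20 = 51 points; 71 − 18 = 53 points; at the midpoint 71 − 19 = 52 points.

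**Step 2: chance imbalance.** With K such patients placed at random into arms of 10, the probability of counts (a, b, c) is C(10,a)·C(10,b)·C(10,c)/C(30,K). Summing this over the counts that differ by three or more gives the first two result columns of the table.

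**Step 3: variance explained.** With q = K/30, gap d and overall rate m = q·p₁ + (1 − q)·p₀, R² = q(1 − q)d²/[m(1 − m)]. The equivalent gain in sample size is 1/(1 − R²) − 1. For K = 6: m = 0.2 × 0.19 + 0.8 × 0.71 = 0.606, R² = 0.16 × 0.2704/0.2388 = 0.181, gain = 1/0.819 − 1 = 22%.

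| K of 30 | Given nitrite arm v control differs by ≥3 | Either nitrite arm v control differs by ≥3 | R² (71% v 19%) | Gain |
|---|---|---|---|---|
| 6 | 17% | 27% | 0.181 | 22% |
| 9 | 23% | 36% | 0.230 | 30% |
| 12 | 26% | 41% | 0.260 | 35% |
| 15 | 27% | 42% | 0.273 | 38% |

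**Step 4: size of the shift.** A difference of 3 in 10 moves the expected difference in insulin independence by 0.3 × 52 = 15.6 points with no drug effect (15.3 to 15.9 over the cited range). For scale, the standard error of a 10 v 10 difference at a rate near 50% is √(2 × 0.25/10) = 0.22, or 22 points.

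**Step 5: smaller gaps.** The same formula with assumed rates of 40% v 10% gives R² of 0.064 to 0.120 and a gain of 7-14%. With 30% v 10%, R² is 0.033 to 0.063 and the gain 3-7%.

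**Step 6: the degree of freedom.** A rough allowance multiplies 1/(1 − R²) by 26/27. At the cited rates the gain becomes 18% (1.221 × 26/27 = 1.18) to 32% (1.376 × 26/27 = 1.32). At 30% v 10% with K = 6 it vanishes (1.034 × 26/27 = 0.996).

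**Step 7: logistic regression.** Under the cited rates with no drug effect, the chance that one surgical-history group has all or no events, so that its coefficient cannot be estimated, is about 0.81⁶ = 28% for K = 6. For K = 15 it is 0.81¹⁵ + 0.71¹⁵ = 0.042 + 0.006 = 5%.

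**The case against.** **Validity.** A reader might infer that omitting surgical history biases the comparison or invalidates the test. The documents do not support that. Patients are randomised, so imbalance is as likely to favour one arm as another. In a simulation at 71% and 19% with no drug effect, the unadjusted test's error rate was 4.6-4.7%. The 16-point shift is below one standard error, so it is part of the sampling error that the test already allows for. This stands: the loss is in precision.

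**Transport.** A reader might also take the 52 points as a known causal effect of earlier pancreatic surgery in this trial. They are an observational contrast from one centre. The two groups are not complements: patients with other abdominal or pancreatic operations have no stated rate. The documents do not say whether that series resembled the insulin-dependent patients of section 3.1, nor give its follow-up time. Insulin independence is not itself a listed endpoint, and no prognostic strength is given for glucose, HbA1c or insulin dose. All of this stands, so every size given here is conditional.

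**Practical gain.** For an assumed 20-point drug effect, simulated power rises only from 14% to 15% (6 of 30 operated) or from 13% to 17% (15 of 30). Adjustment does not rescue a trial of this size. The study also calls itself a pilot. Both points limit the weight of the concern, but the change costs very little.

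**Silence.** Section 4.2 does not say that there are no strata, and the variable list in 7.0 may be cut by text extraction. The analysis sentences, however, are complete and name no adjustment.

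**Conclusion.** The point holds as a missed and inexpensive gain in precision. The plan cites a strong baseline predictor, admits the patients concerned, and pre-specifies no adjustment.

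The probabilities of imbalance (17-27% for one comparison, 27-42% for either) rest only on the assumed 20-50% share. The 16-point shift and the 22-38% gain further require that the cited rates apply to these patients and to an insulin-independence outcome. If the gap is smaller, the gain may be 3-14%, and at the bottom of that range the lost degree of freedom cancels it. For the continuous endpoints the gain cannot be computed from the documents.

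**What to change.** **Section 7.0, data.** Record surgical history before randomisation. Define it in writing as an earlier Puestow procedure or distal pancreatectomy, yes or no, so that it matches the group for which the background gives a rate.

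**Section 7.0, continuous endpoints at 3 months.** Pre-specify this item as a covariate in a linear model (ANCOVA or repeated measures). Add the pre-operative or pre-infusion value of the same measure where it is drawn: HbA1c and C-peptide both are.

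**Section 7.0, binary endpoint (diabetes or insulin use).** Use an analysis stratified by surgical history, for example Mantel-Haenszel or an exact stratified test. Avoid a logistic model with several covariates, given step 7.

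**Islet yield.** Do not adjust for it, although the background names it as a predictor. It is measured after the pre-isolation infusion and could be affected by it.

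**Section 4.2.** Stratifying the randomisation on the same item is optional. With 30 patients it trades better balance on this factor against uneven arm sizes from incomplete blocks.

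**Cost.** One history item per patient and one or two degrees of freedom. The choice should be fixed before unblinding.
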